10.3.4 Removal of Patients From the Study

Patients will be advised that they are free to withdraw from the study at any time. If necessary, the Investigator may withdraw a patient from the study to protect the health of that patient. In case of early termination the Investigator will fully document the reason for early termination. The clinical report will include all reasons for early withdrawals. Reasons for removal may include the following:

- Patient withdrew consent.
- Significant AE that led the Investigator or patient to withdraw for safety reasons.
- Non-compliance with protocol requirements (e.g., use of restricted medication, not following dosing procedures, failure to make scheduled study visits in a timely fashion).
- Presence of live lice at any post-treatment visit.
- Participant enrolls in another clinical trial during the study, or is found to have previously enrolled in this clinical trial.

If a randomized patient terminates from the study early, all efforts will be made to complete the End of Study procedures. Patients who withdraw or are removed from the study will not be replaced.

CONFIDENTIAL PROTOCOL

A Randomized, Double-Blind, Placebo-Controlled, Parallel-Design, Multiple-Site Clinical Study to Evaluate the Therapeutic Equivalence and Safety of Ivermectin Lotion 0.5% (Actavis Laboratories UT, Inc.) to SKLICE® (ivermectin) Lotion, 0.5% (Arbor Pharmaceuticals, LLC) in the Treatment of Human Head Lice Infestation

10.4 Treatments

10.4.1 Treatments Administration

Patients will be provided with verbal and written instructions on how to administer the study product at home. At Visit 1, eligible patients will receive a 4 oz (117 g) tube of randomized study product (i.e., Test, Reference or Placebo). Study product should be applied on the day of or the day after enrollment into the study. The day of dosing will be considered Day 1. Patients, infested household members, and/or caregivers will be instructed to apply the study product to dry hair in an amount sufficient (up to 1 tube) to thoroughly coat the hair and scalp, avoiding contact with the eyes. Study product should be left on the scalp for 10 minutes before rinsing with water only. Patients should wash their hands after application of the study product. Hair should be allowed to dry naturally (pat drying with decontaminated towel is permitted) and left uncovered after application of the study product. Following application and rinsing of the study product, patients may not shampoo, wash, or rinse their hair or scalp until the Day 2 visit has been completed.

If any non-infested household member is pregnant or lactating at the time of the study, this person may not be involved with application of the study product to any household members.

The study product should be applied as a single dose. Patients should not use the product more than once. Tubes of study product will be collected at Visit 2 and the site will verify the product was used and rinsed. If a patient inadvertently does not return a tube of study product at its respective return visit, the patient should be instructed to return it as soon as possible or at the next visit.

On Day 1, before applying treatment, all bedding, hats, clothing, and towels used by infested persons or their household, sexual, and close contacts in the two days before treatment should be decontaminated by machine washing in high temperatures (at least 150°F) and drying in a hot dryer for at least 20 minutes (additional time should be added if large loads are dried). Clothing or items that are not washable can be dry-cleaned or sealed in a plastic bag and stored for two weeks. Personal care items such as combs, brushes, and hair clips should be washed in hot water (at least 135°F) for 10 minutes. Instructions on good hygiene and proper methods of decontamination will be provided to the patient and caregivers.

10.4.2 Identity of Investigational Product

The following products will be used in the study:

- **Test:** Ivermectin Lotion, 0.5% (Actavis Laboratories UT, Inc.)
- **Reference:** SKLICE® (ivermectin) Lotion, 0.5% (Arbor Pharmaceuticals, LLC)
- **Placebo:** Placebo (vehicle) lotion (Actavis Laboratories UT, Inc.)

10.4.3 Study Product Shipment, Storage, and Retention

An individual tube of study product (i.e., Test, Reference or Placebo) will be packaged, as a patient kit. Each patient will be assigned to one patient kit. [REDACTED]

[REDACTED] The study product will be blinded, packaged and delivered to the site in bulk. The study

CONFIDENTIAL PROTOCOL

A Randomized, Double-Blind, Placebo-Controlled, Parallel-Design, Multiple-Site Clinical Study to Evaluate the Therapeutic Equivalence and Safety of Ivermectin Lotion 0.5% (Actavis Laboratories UT, Inc.) to SKLICE® (ivermectin) Lotion, 0.5% (Arbor Pharmaceuticals, LLC) in the Treatment of Human Head Lice Infestation

products will be shipped to each Investigator's site from a centralized location. The Principal Investigator at each site is responsible for ensuring that all study products are stored in a locked, secure location, with access limited to the Investigator and his/her designee(s). An accurate inventory of the study product will be maintained in accordance with federal regulations.

Study product is to be stored in a secure, locked location, at room temperature between 20-25°C (68°F to 77°F) with excursions permitted to 15°-30°C (59°-86°F). Any excursions from the permitted excursion range of 15°-30°C (59°-86°F) will require prompt notification to [REDACTED], and thereafter [REDACTED] will notify the Sponsor.

For every study product shipment received at the investigative site, the Investigator (or designee) will randomly select study product kits for retention, unless otherwise instructed by the Sponsor and/or [REDACTED]. The selection process will ensure a sufficient amount of retention samples are retained as per Sponsor requirement. These kits will be affixed with a label provided by [REDACTED] to be clearly marked as retention samples and are not to be used for dispensing to study patients. The selected retention samples will be retained at a third party storage facility [REDACTED] [REDACTED] under FDA regulations as study retention samples.¹⁷

Once the site has been notified that they may do so, all unused study product and empty or partially used tubes of study product, other than that randomly selected for retention samples will be returned to the Sponsor (Actavis) or designee. It is important that retention samples not be returned to [REDACTED], the Sponsor or the packaging company during or at the end of the study. Sufficient study product tubes must be retained among the sites participating in the study to meet the sample retention requirements as outlined by the FDA.¹⁷

10.4.4 Method of Assigning Patients to Treatment Groups

The study product will be randomized, packaged and blinded by an independent packaging company [REDACTED]. The randomization will be pre-planned according to a computer-generated randomization schedule. [REDACTED]

Using [REDACTED] (IWRS), all eligible and non-eligible patients who are consented and screened into the study will be assigned a patient number. The patient number is assigned after a patient is consented. It is the only identifier for screened patients. [REDACTED]

[REDACTED] The system will also assign a study product kit number (based on the randomization schedule created by an independent biostatistician). The study product kit number is the identifying number listed on the study product dispensed to eligible patients. [REDACTED]. This will be the identifier used for randomized patients (i.e., randomization number). Both the patient number and randomization number will be entered into the patient's eCRF. At the end of the

CONFIDENTIAL PROTOCOL

A Randomized, Double-Blind, Placebo-Controlled, Parallel-Design, Multiple-Site Clinical Study to Evaluate the Therapeutic Equivalence and Safety of Ivermectin Lotion 0.5% (Actavis Laboratories UT, Inc.) to SKLICE® (ivermectin) Lotion, 0.5% (Arbor Pharmaceuticals, LLC) in the Treatment of Human Head Lice Infestation

study, after all the clinical data have been entered and the study database has been locked, a copy of the randomization schedule will be sent to the statistician.

10.4.5 Study Blind

The Investigator, staff at the study site, study monitors, and data analysis/management personnel will be blinded to the patient assignment. Each study site will have at least one Independent Dispenser. The role of the Independent Dispenser is to dispense and collect study product to/from the patients, maintain dispensing records, and ensure the study product logs are complete and accurate. The patient will be requested not to discuss the appearance of the study product with the Investigator or study staff outside of the Independent Dispenser.

[REDACTED]

[REDACTED]. The Test, Reference and Placebo products will be blinded with identical outer cartons and labels. This will allow the study to be conducted under double-blind conditions (i.e., such that neither the patient nor the Investigator nor study staff members will know the identity of the patient's treatment).

To ensure that information that could potentially bias handling of data is not disclosed, the packaging company will hold the randomization scheme until after database lock. During the clinical phase of the study, [REDACTED] IWRS includes a form for Investigators to complete to determine treatment assignment (i.e., to unblind individual patient) to be completed for a medical emergency only.

[REDACTED]

Whenever possible, the [REDACTED] Medical Monitor should be contacted before breaking the blind for any patient. If the Medical Monitor cannot be reached, then the Vice President Clinical Trials and Data Management or designee will be contacted before unblinding. Investigative sites can use either one of the above methods to unblind a patient, when unblinding is deemed necessary by the Principal Investigator.

In the event the blind is broken for any reason, Sponsor and [REDACTED] will be notified as soon as possible in writing of the details of the occurrence.

At the conclusion of the study, after the database has been locked, each site will be sent a sealed envelope containing the full study randomization scheme that should be retained with the study documents in the event of an FDA inspection.

10.4.6 Compliance

Patients will be provided with a diary to record the time and date of dosing, other concomitant medications, and AEs. Patients who do not dose as instructed on Day 1 will be considered non-

CONFIDENTIAL PROTOCOL

A Randomized, Double-Blind, Placebo-Controlled, Parallel-Design, Multiple-Site Clinical Study to Evaluate the Therapeutic Equivalence and Safety of Ivermectin Lotion 0.5% (Actavis Laboratories UT, Inc.) to SKLICE® (ivermectin) Lotion, 0.5% (Arbor Pharmaceuticals, LLC) in the Treatment of Human Head Lice Infestation

compliant with dosing, and excluded from the per-protocol (PP) population. Dosing compliance will be checked based on the dosing diary entry and verbal discussion with the patient at Visit 2.

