10.5.2 Visit 2 (Day 2): Interim Visit

Visit 2 must occur the day after patient dosing. All treated household members will return for follow-up at Visit 2 only.

1. **Concomitant Medication:** Review the patient's use of any new or ongoing concomitant medications since the last visit.
2. **Adverse Events:** Patients will be questioned about any health status changes/AEs since last visit. All AEs will be recorded.
3. **Vital Signs:** The patient's vital signs will be recorded (pulse, blood pressure, temperature and respiration rate).
4. **Pregnancy Test:** A urine pregnancy test will be required of all female patients of childbearing potential.
5. **Louse Examination:** An Investigator or staff member, who is experienced and trained in detection and evaluation of head lice, will perform a visual inspection for the presence of live lice (i.e., live adults and/or nymphs). Louse examination should be conducted for 15 minutes or longer, unless any live lice are detected in less time. If any live lice are found during the exam, the patient should be discontinued and provided with alternative therapy. Duration of examination and number of live lice should be recorded in the patient's eCRF.
6. **Application Site Reactions:** Patients will be asked about any application site reactions since last visit (see Appendix A). Any reactions will be recorded.
7. **Ocular Irritation Assessment:** Patients will be questioned about any ocular discomfort resulting from contact with the study product. Any discomfort will be documented as an AE.
8. **Return Study Product:** Patients will return the used study product tube.
9. **Collect and Review Patient Diary:** Study staff will collect previously provided diary and review for compliance with the protocol.
10. **Provide Patient Diary:** A diary will be provided to record AEs and concomitant medications.

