10.6.12 Collect Study Product

Tubes of study product will be collected from all patients at Visit 2 and checked for compliance or evidence of tampering with the blind.

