11.3 Study Populations

11.3.1 Per-Protocol Population

The PP population will include all randomized patients who:

- Meet all inclusion and exclusion criteria.
- [Redacted]
- [Redacted]
- Have no significant protocol deviations.
- Apply the study product as instructed on Day 1.

A large rectangular black box used to redact sensitive information from the document.

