11.3.2 Modified Intent-to-Treat (mITT) Population

The mITT population will include all randomized patients who meet all inclusion/exclusion criteria, apply the study product as instructed, and return for at least one post-baseline evaluation visit.

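### Nothing in the readable text keeps the Visit 2 dosing-compliance call, which gates the PP and mITT sets, independent of the louse result found at the same visit

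*Protocol*

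**What the plan says.** **How compliance is judged.** Protocol 10.4.6: "Dosing compliance will be checked based on the dosing diary entry and verbal discussion with the patient at Visit 2". The same section excludes non-compliant patients from the PP population. Two further sections make the returned tube part of the evidence. In 10.4.1, "Tubes of study product will be collected at Visit 2 and the site will verify the product was used and rinsed"; in 10.6.12, "Tubes of study product will be collected from all patients at Visit 2 and checked for compliance or evidence of tampering with the blind". Under 10.4.5, an Independent Dispenser collects the product.

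**What it decides.** One PP criterion in 11.3.1 is "Apply the study product as instructed on Day 1". The mITT set in 11.3.2 is limited to eligible randomized patients who "apply the study product as instructed, and return for at least one post-baseline evaluation visit". SAP section 6 repeats both definitions. Protocol 11.6 and SAP 8.2.1 decide equivalence on the primary endpoint in the PP set alone.

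**Where it sits in the visit.** In the 10.5.2 list the louse examination is item 5, with the instruction "If any live lice are found during the exam, the patient should be discontinued and provided with alternative therapy". Tube return is item 8. Item 9 reads "Study staff will collect previously provided diary and review for compliance with the protocol".

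**What is masked.** The blind in 10.4.5 covers treatment assignment. It does not cover the louse result.

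**The concern.** Being compliant means following the application instructions in 10.4.1: enough product to coat hair and scalp, ten minutes' contact, rinsing with water, and no washing until the Day 2 visit is over. The diary's dosing entries are only date and time (10.4.6, 10.6.13). The other elements must largely come from recall in the conversation, and no readable passage gives an operational threshold for them. For young children an adult in the household completes the diary (10.6.13), and the index patient is by definition the youngest randomized household member.

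If the conversation follows the examination, both sides know whether lice survived. Finding live lice naturally prompts a question about whether the product was applied properly; finding none does not. A judgment call that removes patients from the analysis could then depend on the outcome. Treatment blinding does not prevent this, because the trigger is the visible result. Removal need not differ by arm to matter: at the success rates an effective product would be expected to show, removing the same share of failures from Test and Reference narrows the gap between them. In an equivalence trial, that is the direction that favours the claim.

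**Working it through.** **1. The plan's own figure.** No stated number is in dispute. The planned size of about 378 index patients (synopsis) cannot be reproduced, because the expected rates, power, allocation ratio and dropout are redacted or not given.

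**2. Inputs.**
- Margin of ±20 points and 90% confidence interval: Protocol 11.6, SAP 8.2.1.
- Interval: difference ± 1.645 × se, with se = √[P_T(1−P_T)/n_T + P_R(1−P_R)/n_R], from SAP 8.2.1.
- Assumed: 126 per active arm (378/3, before any other PP exclusions).
- Assumed: true success of 75% on Reference and 55% on Test, exactly at the margin.
- Assumed: share f of all Day 15 failures removed as non-compliant, equal in both arms, with no successes removed.

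**3. Effect on the observed rates.** Observed success = p / [1 − (1−p)f]. For f = 0.20, Test is 0.55/0.91 = 60.4% and Reference is 0.75/0.95 = 78.9%, a gap of 18.5 points. The last column is the simulated chance that the whole SAP interval lies within ±20 points; simulation error can move its last digit by 0.1.

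| f | Test | Reference | Gap (points) | False equivalence |
|---|---|---|---|---|
| 0 | 55.0% | 75.0% | 20.0 | 4.9% |
| 5% | 56.3% | 75.9% | 19.7 | 5.5% |
| 10% | 57.6% | 76.9% | 19.3 | 6.2% |
| 20% | 60.4% | 78.9% | 18.5 | 8.2% |
| 30% | 63.6% | 81.1% | 17.5 | 11.2% |

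**4. Sensitivity to the assumptions.** With Reference success of 70–90%, Test 20 points lower, and 126 or 151 per active arm (378 split 1:1:1, or 2:2:1 giving 378 × 2/5 = 151), false equivalence is 4.7–5.3% with no removal. It is 5.2–7.0% at f = 5%, 5.7–9.2% at 10%, 7.0–15.7% at 20% and 9.0–26.7% at 30%.

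**5. Who is exposed.** Patients lice-free at Visit 2 have their compliance checked before they fail at Visit 3 or 4. If v is the share of all failures visible at Visit 2 and s the share of those removed because of the finding, then f = v × s. The documents do not give v. If v were one half, f = 10% to 30% needs s = 20% to 60%; if one third, s = 30% to 90%.

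**6. When the gap narrows.** The formula in step 3 compresses differences where (1−f)/[1−(1−p)f]² is below 1, that is for p above 1 − [1−√(1−f)]/f. This is 0.49 at f = 5% and 0.47 at f = 20%. For two rates 20 points apart, their midpoint must lie above roughly one half. Below that the gap widens: with f = 20%, 50% v 30% becomes 55.6% v 34.9%, or 20.7 points.

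**7. Superiority in mITT.** With f = 20%, 75% v 20% moves from 55.0 to 55.1 points, and 75% v 40% from 35.0 to 33.5.

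**The case against.** The strongest reply is that the protocol prescribes no wrong order. The items in 10.5.2 are numbered but not said to be sequential. The study schematic lists providing the diary before collecting it, while 10.5.2 lists collection first, so list position is weak evidence of practice. This stands: the gap is that no order, and no assessor unaware of the louse result, is required.

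Second, there is evidence that does not depend on the conversation. The diary is meant to be filled in at home, and the tube is checked. This also stands in part. A tube can reveal that the product was not used, but not contact time or washing, and its return is likewise listed after the examination.

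Third, two PP criteria and a further block in 11.3.1 are redacted, and Appendix E records that the PP criteria were updated. A rule protecting early failures may be there, so the PP part of this point carries that reserve. The readable mITT definition contains no such rule.

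Three stronger readings are tempting and unsupported:
- **That failures will be removed.** The documents show an opportunity, not a practice. They do not say what the conversation covers.
- **That a product at the margin would pass once its observed gap falls below 20 points.** The whole interval must lie inside the margin. At f = 20% the expected group sizes are 126 × 0.91 = 114.7 and 126 × 0.95 = 119.7, se is 5.89 points, and the lower limit is −18.5 − 1.645 × 5.89 = −28.2. An observed gap of 18.5 points would fail.
- **That removing failures always favours equivalence.** Step 6 of the working shows that this depends on the success rates, and the planning rates are not readable.

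**Conclusion.** The point holds as a gap in safeguards. Dosing compliance decides membership of both efficacy sets and rests partly on judgment, and nothing readable separates that judgment from an outcome seen at the same visit. In the 75% v 55% illustration, the false-equivalence rate moves from 4.9% to between 5.5% and 11.2% for 5% to 30% of failures removed. The lower end is more realistic, because only failures visible at Visit 2 are exposed. These figures rest on assumed success rates, allocation and removal shares, none of which the documents give, and on equal removal in both arms. The effect on superiority is small. Because the remedy is cheap and the PP set alone decides equivalence, it is worth making as an improvement; it is not evidence that the planned analysis is invalid.

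**What to change.** In Protocol 10.5.2 and 10.4.6:
- Place tube return, diary review and the dosing questions before the louse examination, and state that this order is required.
- Record the compliant or non-compliant classification, with its time, in the source document before the examination starts.
- State in Protocol 11.3 and SAP section 6 that this entry determines the dosing criterion for the PP and mITT sets.
- Allow a later change only on objective new evidence, such as a tube returned late as 10.4.1 permits. Document the reason, and make the decision before unblinding.

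The cost is a small change in visit flow and one timed source entry; no visit or procedure is added. Using the source document fits 12.2.4, under which eCRFs are completed from source. The change cannot mask the result from a family that has already seen lice at home, so it reduces the risk without removing it.

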10.5 Study Conduct

Unscheduled visits will be allowed as deemed necessary by the Investigator or Sponsor to ensure patient safety or to perform other study-related procedures.

10.5.1 Visit 1 (Day -1 to 1): Screening/Baseline

1. **Informed Consent:** Patients who are willing to comply with study procedures will read and sign the ICF, as appropriate. Patients who are considered minors will read and sign the assent to participate form, as appropriate, and their parent or legal guardian must sign the ICF. Patient's 11-17 years of age will read and sign an IRB-approved assent form and patients 6-10 years of age will provide verbal assent. Patients 6 months-5 years of age will be exempt from providing assent based on the child's comprehension and cognitive skills. All infested members of a household must agree to receive treatment for anyone in the household to be enrolled.
2. **Medical History and Baseline Demographics:** Review the patient's demographic and medical history.
3. **Concomitant Medication:** Review the patient's use of any medications in the last four weeks.
4. **Vital Signs:** The patient's vital signs will be recorded (pulse, blood pressure, temperature and respiration rate).
5. **Pregnancy Test:** A urine pregnancy test will be required of all female patients of childbearing potential before enrollment.
6. **Louse Examination:** An Investigator or staff member, who is experienced and trained in detection and evaluation of head lice, will perform a visual inspection for the presence of live lice (i.e., live adults and/or nymphs). Louse examination should be conducted for 15 minutes or longer, unless any live lice are detected in less time. Duration of examination and number of live lice should be recorded in the patient's eCRF.
7. **Inclusion/Exclusion Criteria Review:** Study staff will confirm that the patient meets all inclusion/exclusion criteria.
8. **Application Site Reactions:** The Investigator will grade the individual signs and symptoms presented in Appendix A. This will serve as a baseline for subsequent assessments of application site reactions.
9. **Dispense Study Product:** Eligible patients will receive one tube of study product with instructions for dosing at home. Tubes will be dispensed for all members of a patient's household.

CONFIDENTIAL PROTOCOL

A Randomized, Double-Blind, Placebo-Controlled, Parallel-Design, Multiple-Site Clinical Study to Evaluate the Therapeutic Equivalence and Safety of Ivermectin Lotion 0.5% (Actavis Laboratories UT, Inc.) to SKLICE® (ivermectin) Lotion, 0.5% (Arbor Pharmaceuticals, LLC) in the Treatment of Human Head Lice Infestation

10. **Provide Patient Diary:** A diary will be provided to record date and time of dosing, AEs, including any ocular discomfort, and concomitant medications.

11. **Adverse Events:** Patients will be questioned about any AEs that occurred during the visit.

